- DLss testing per the following protocol

We anticipate the total testing will take 30 minutes or less

 - 1) Subjects will be comfortably seated in a treatment recliner or in a gurney in a private room in the Stanford CTRU. Patient and the examiner will wear safety goggles. The door will be closed. The areas of skin to be tested will be shaved to avoid differences in light absorption and heating, because stimulation is non-contact; but strong pigmentation spots, tattoos, and moles will be avoided.

- 2) Patients will be reminded that if pain becomes too difficult for them to tolerate, they can stop the testing at any time.
- 3) The skin on the dorsum of the foot will be marked with a pen denoting 10mmx10mm squares.
- 4) The skin temperature will be monitored by infrared thermometer before the test and every 5 minutes during testing. If skin temperature is below 33 C, the skin tissue will be heated with warmed towels and maintained to keep temperature +/- 0.5 °C.
- 5) Each patient will have an A and C fiber stimulation. Stimulation will be performed on the dorsum of the foot using stimulation previously published parameters to elicit “burning pain,” which is from activation of C-fibers and “pinprick” pain from A-fibers:
 - A_δ fiber protocol*: 60-millisecond duration, 980-nm stimuli, 1-mm diameter stimuli
 - C fiber protocol*: 2-second duration, 980-nm stimuli, 5-mm diameter stimuli
- 6) Stimulation will begin at 600mA±2 current (if sensation is felt at 600mA±2, go down two levels or 400mA±2) and increased at 100mA±2 increments until the subject identifies the stimulation as painful. The current will be increased up to a maximum of 1650 mA for the C-fiber protocol and to a maximum of 3500 mA for the A_δ-fiber protocol. In rare cases, patients may have pain thresholds that exceed the maximum skin temperature considered safe. For these patients, we will use the maximum safe stimulus level (3500 mA for the A_δ fiber, 1650 mA for the C fiber) to calculate the A_δ:C ratio. For subsequent runs, start at the highest level that do not evoke sensation from prior run (if sensation is felt at that level, go down two levels or 200mA ±2)

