- 7) The pain threshold will be obtained using the “method of levels”, using a series of ascending stimulation from energy that does not evoke sensation (600mA) and increasing by steps of 100mA until the last sensation is recorded as a 30-40 on the 0-100 pain scale. (0= no sensation, 10= definite sensation/pain, 100 worst imaginable pain). The procedure will be repeated three times and the pain threshold will be defined as averaging the readings of the 3 successive stimulations. The selected current will be applied 4 times. At this current, we expect to produce pain 50% of the time, and no pain 50% of the time.
- 8) The area of stimulation will be moved by 5 millimeters between each stimulation according to the grid (see #3).

Study Visit 2 (21 weeks +/- 2 weeks after first dose of chemotherapy for ovarian cancer)

- Concomitant medications as above
- Cumulative chemotherapy dose as above
- Headache assessment as above
- Pain inventories as above
- DLss testing as described above

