4.5 Prior Validation of the DLss

Laser stimulation, similar to what is being used in the DLss, has been used in pain clinics

and research since 1975 as a diagnostic test. It has been proven to be useful and safe. Laser irradiation simultaneously activates both A delta and C fibers and primarily heat fibers located in the epidermis (up to 50-150 micron depth)(47-49).

Diode laser stimulation (the DLss used in this protocol) provides relatively uniform heating of skin from 50 to 600 microns deep, allowing for a distinct, singular burning or singular pricking pain depending on the laser pulse parameters. Experiments using an infrared diode laser conducted in Stanford and another institutions have shown that a short and a long laser pulse produces, respectively, a singular pinprick sensation (representing A-delta stimulation), and a singular burning pain sensation (representing C fiber stimulation) when applied to the dorsal hand skin of healthy subjects and pain patients volunteers. These preliminary results show that diode laser stimulation can safely and selectively activate A delta and C thermos-nociceptors(20, 22, 23, 50).

Diode lasers similar to the one used in this study are FDA approved and are often used in cosmetic medical procedures for hair removal. The lasers used for cosmetic procedures are set at *ten times* the power density of that used in our study.

Over 115 subjects have been tested with the DLss. No patient has withdrawn from DLss testing due to pain. Two patients had pin-tip sized skin discolorations that resolved in the course of a week.

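### Does entering the stimulus limit as the threshold for capped patients, with no cap count or sensitivity analysis, undermine the Aδ:C ratio?

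*Combined protocol and SAP*

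**What the plan says.** Section 4.4, step 6, starts at 600 mA, with the current "increased at 100mA±2 increments until the subject identifies the stimulation as painful". On the limits: "The current will be increased up to a maximum of 1650 mA for the C-fiber protocol", and up to 3500 mA for Aδ. It anticipates the problem: "In rare cases, patients may have pain thresholds that exceed the maximum skin temperature considered safe". The remedy is substitution: "For these patients, we will use the maximum safe stimulus level", that is, 3500 mA or 1650 mA goes into the ratio.

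Step 7 ends a run by a rating, "until the last sensation is recorded as a 30-40 on the 0-100 pain scale". The procedure is done three times, and "the pain threshold will be defined as averaging the readings of the 3 successive stimulations". It does not say what to do when only one or two of the three runs reach the limit.

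Section 5.2 compares the groups' mean log ratios by a two-sided t-test and uses the visit 1 ratio in a logistic regression on pain at visit 2. Section 5.1.2 adds a Spearman correlation. None of Sections 5.1 to 5.3 mentions limit-valued thresholds. Section 6.1 says that case report forms will be developed; it does not list their fields.

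**The concern.** A threshold known only to exceed a limit is right-censored, and treating it as exact biases a mean. Here the outcome is a ratio of two such quantities. A cap on Aδ alone pulls it down, a cap on C alone pushes it up, and a patient capped on every run of both fibers scores 2.12 whatever the truth. If cap rates differed between Groups A and B, the Aim 1 contrast would absorb the difference, and the Aim 2 logistic regression uses the same values. (The Spearman analysis uses ranks and is less exposed.)

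Two gaps seem to hide the effect. The substitution rule is written for patients, but the threshold is a three-run mean, so a partly capped patient could be scored in two ways. And 3500 mA is an ordinary step on the 100 mA ladder, so the current alone cannot separate a painful response at 3500 mA from an endpoint never reached. The protocol gives no rate to support the word rare.

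**Working it through.** **The plan's own figure.** Inputs from Section 5.3: 25 per group, log SD 0.33, fold 1.31. Two-sided α = 0.05 is assumed, since the plan does not state it. With δ = ln 1.31 = 0.270, the noncentral-t power of the two-sample t-test is 80.9%, so the stated 80% reproduces.

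**Simple arithmetic on the rule.**
- Both fibers fully capped: 3500/1650 = 2.12.
- Ladder from 600 mA: (3500 − 600)/100 = 29, a whole step; (1650 − 600)/100 = 10.5, not a step.
- Partly capped example, Aδ readings 3000, 3200 and one run at the limit. Limit entered for that run: (3000 + 3200 + 3500)/3 = 3233 mA. Limit entered for the patient: 3500 mA. Quotient 3500/3233 = 1.08, an 8% difference in that patient's ratio.
- Effect on the trial: ln 1.08 ≈ 0.079; 0.079/25 = 0.003 in the group mean log ratio. A fold of 1.310 becomes 1.310 × exp(0.003) = 1.314.
- A larger error: a true Aδ threshold 1.5 times the limit costs ln 1.5 = 0.405 in one patient's log ratio, and 0.405/25 = 0.016 in the Group A mean. Five such patients among 25 cost 0.081, which takes 1.31 to 1.31 × exp(−0.081) ≈ 1.21.

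**Simulation of the planned analysis.** The documents give no absolute thresholds, so these are assumptions: log-normal runs, three per fiber; log SD 0.33 for each fiber's three-run mean and for the ratio; run-to-run log SD 0.10 or 0.20; true fold 1.31 through Aδ in Group A; equal C thresholds in both groups; each capped run entered at the limit and then averaged. Paired entries are for run SD 0.10 / 0.20.

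| Group B medians Aδ/C (mA) | Highest share of patients with a capped run, any group and fiber | Fold from planned ratio |
|---|---|---|
| 1200/900 | 6 / 10% | 1.309 / 1.308 |
| 1400/1000 | 11 / 17% | 1.306 / 1.301 |
| 1600/1100 | 17 / 25% | 1.296 / 1.295 |
| 1800/1100 | 18 / 25% | 1.287 / 1.281 |
| 2200/1300 | 38 / 47% | 1.244 / 1.238 |

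Power under substitution was 82 to 83% in the first three rows and 79 to 80% in the last, against 80 to 82% with no cap. The limit trims the spread of the ratio as well as its mean, so power hardly moves. In the first three rows C is capped more often than Aδ (first row: Group A Aδ 2 / 3%, C 6 / 10%), but almost equally in both groups, so its effect largely cancels. All runs capped on both fibers, the 2.12 case, occurred in at most 0.5% of Group B patients in the first four rows and in 1.4 to 2.5% in the last.

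**Can a cap be recognised?** Not from an Aδ current of 3500 mA alone. But step 7 ends a run on a pain rating. A run at 3500 mA rated 30 to 40 is a response; one rated lower is a cap. For C, a reading of 1650 mA lies off the ladder and points to the limit by itself.

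**The case for a change.** The strongest case is that equal rules do not give equal cap rates, and that the bias need not be conservative. Suppose there is no true difference in ratio but both thresholds are 0.27 log units higher in one group, with C capped in 10% of one group and 46% of the other. The t-test then rejects in 12% of trials instead of 5%. That result is correct, but it needs nearly half of one group capped on C. With C caps of 2% and 19% the rejection rate is 5.6%. It also needs C thresholds raised in one group, whereas the preliminary work in Section 2.0 reports C thresholds similar to healthy volunteers in painful neuropathy. That comparison was not with Group B, so the pattern is indicative only.

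It can also be said that rare is unsupported, because Section 4.5 describes earlier results "when applied to the dorsal hand skin of healthy subjects and pain patients volunteers" while here "Stimulation will be performed on the dorsum of the foot". The Section 4.5 sentence concerns the quality of the sensation, not thresholds or cap rates, so it shows nothing about how often the limit will be reached.

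What stands is narrow. The text does not say that the rating is kept with each run's current, does not state the averaging rule for a partly capped patient, and asks for no cap count. The case report forms are not shown, so their content cannot be judged either way. A joint censored model would recover the fold of 1.31 in the simulation, but the data were generated from that same model. In the two scenarios with least capping its fold differed from the substituted one by more than 5% in only 0 to 0.3% of trials.

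**Conclusion.** No change to the plan is needed. Substitution at the limit is specified in advance, is blind to group, and keeps capped patients in the analysis. If capping is rare, as the protocol expects, the Aim 1 fold stays at 1.308 to 1.309 against a true 1.31 and power is not reduced. A material bias needs capping on a scale that contradicts that premise and would be plain from the readings.

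The missing detail has an obvious completion. Step 7 averages readings, so a run that reaches the limit enters at the limit and the three are then averaged; the other reading moves the fold by 0.004 for one patient in 25. Keeping the rating beside the current on forms still to be developed identifies a cap, and any competent report would give the counts. If capping proved common, a labelled sensitivity analysis treating capped runs as right-censored could be added then, with the primary t-test as it is.

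The conclusion rests on the protocol's statement that capping is rare, and on assumed threshold levels, because the documents give none.

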4.5 Prior Validation of the DLss

Laser stimulation, similar to what is being used in the DLss, has been used in pain clinics

and research since 1975 as a diagnostic test. It has been proven to be useful and safe. Laser irradiation simultaneously activates both A delta and C fibers and primarily heat fibers located in the epidermis (up to 50-150 micron depth)(47-49).

Diode laser stimulation (the DLss used in this protocol) provides relatively uniform heating of skin from 50 to 600 microns deep, allowing for a distinct, singular burning or singular pricking pain depending on the laser pulse parameters. Experiments using an infrared diode laser conducted in Stanford and another institutions have shown that a short and a long laser pulse produces, respectively, a singular pinprick sensation (representing A-delta stimulation), and a singular burning pain sensation (representing C fiber stimulation) when applied to the dorsal hand skin of healthy subjects and pain patients volunteers. These preliminary results show that diode laser stimulation can safely and selectively activate A delta and C thermos-nociceptors(20, 22, 23, 50).

Diode lasers similar to the one used in this study are FDA approved and are often used in cosmetic medical procedures for hair removal. The lasers used for cosmetic procedures are set at *ten times* the power density of that used in our study.

Over 115 subjects have been tested with the DLss. No patient has withdrawn from DLss testing due to pain. Two patients had pin-tip sized skin discolorations that resolved in the course of a week.

4.6 Potential Adverse Events

While this protocol is not interventional, we recognize the potential for this testing to cause discomfort. Patients will be reminded that they can stop testing at any time.

There is a remote risk of skin injury or burning by laser stimulation when used for pain testing, that occurs by overheating of skin surface. This laser irradiation penetrates the skin fairly deeply, and does not allow overheating of the skin's surface. We also use a short, concentrated pulse; this will activate nerve fiber but is not long enough in duration to cause tissue damage. We have defined pain threshold levels for testing as moderate only, and are therefore only exposing subjects to the minimal stimulation that causes brief, moderate pain.

Over 115 subjects have been tested with the DLss. No patient has withdrawn from DLss testing due to pain. Two patients had pin-tip sized skin discolorations that resolved in the course of a week.

If any patient experiences an adverse event related to testing that is concerning to the study staff, protocol director, or PI; or is previously undescribed, we will report this to the IRB and SRC.

In addition, this protocol will be monitored by the Stanford DSMC.

4.7 Specimens

There are no specimens to be collected in this protocol.

4.8 Tissue for Biomarkers

There is no tissue being used for biomarkers in this study.

5.0 STATISTICAL CONSIDERATIONS

5.1 Outcome Measurements

5.1.1 Outcome Measure for Aim 1

The primary outcome measure of this study is the difference in the “A δ :C pain threshold ratio” for patients with a painless response to chemotherapy versus painful neuropathy, as measured using the DLss.

The “A δ :C pain threshold ratio” is calculated using the A δ -fiber and C-fiber pain thresholds determined using the protocol outlined in **section 4.4**.

Each patient will have 2 testing sessions:

- 1) 9 weeks +/- 1 week from cycle 1, day 1 of chemotherapy
- 2) 21 weeks +/- 2 weeks after first dose of chemotherapy for ovarian cancer

This is not a safety outcome.

5.1.2 Outcome Measure for Aim 2

The second outcome measure of this study is the correlation between the “A δ :C pain threshold ratio” and the development of pain.

We will generate a Spearman correlation coefficient for the “A δ :C pain threshold ratio” obtained at the first testing session and the presence or absence of pain at the time of the second test.

This is not a safety outcome.

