Based on these preliminary data, *we propose that the A δ :C pain threshold ratio, as measured by the DLss during chemotherapy, will identify those patients at risk of developing pain during their treatment.* Ultimately, this will help us identify patients who 1) may benefit from a change in their treatment to prevent CIPN and 2) patients who would be the best candidates for interventional trials testing new drugs for the prevention of PPN.

Aim 1: Demonstrate that the A δ :C pain threshold ratio is significantly higher in patients with painful CIPN than in patients with painless CIPN.

Ovarian cancer annually affects about 20,000 women in the US and causes 14,000 deaths (1999–2012 Cancer Incidence and Mortality Data, <http://www.cdc.gov/cancer/ovarian/statistics/>) (24) Ovarian cancer patients' first line chemotherapy regimen is typically a taxane combined with platinum. These drugs are known to cause CIPN neuropathic symptoms in up to 70% of patients; a large portion of those patients develop painful CIPN (25, 26). The combination of taxane with platinum may increase development of CIPN in 1.5 times compared to just taxane application(25). As a result, ovarian cancer patients have a high overall burden of painful CIPN. Though the exact mechanism of nerve damage may differ between taxanes and platinum drugs, they both result in painful CIPN. Here we will examine the underlying shared pathophysiology

of neuropathic pain. We will evaluate the DLss in [64] ovarian cancer patients with painful and painless neuropathy during initial taxane combined with platinum treatment, to determine their A δ :C pain threshold ratios. Presence or absence of pain will be determined via pain questionnaire and numeric pain scale (27). Enrolling 25 patients with painful CIPN and 25 patients with painless CIPN, we will have 80% power to detect a 1.31 fold A δ :C pain threshold ratio.

Aim 2: Determine the A δ :C ratio over time in patients with CIPN.

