3.2 Inclusion Criteria

- 3.1.1 Have pathologically proven ovarian cancer or cancer of mullerian origin that requires first-line treatment with a taxane + platinum based chemotherapy regimen.
- 3.1.2 GROUP A (painful neuropathy group): Must have subjective symptoms of painful peripheral neuropathy (burning, stabbing, throbbing, painful tingling, aching in the fingers and/or toes) that is greater than or equal to 10 on a scale of 0 to 100 in the neuropathic pain questionnaire
GROUP B (no pain group): Must either have subjective symptoms of painless neuropathy (loss of sensation, worsening balance, strange sensation in fingers and/or toes) or no complaints related to neuropathy.
- 3.1.3 Be ≥ 18 years of age
- 3.1.4 Have a life expectancy of 6 months
- 3.1.5 Ability to understand the study protocol, participate in testing, and the willingness to sign a written informed consent document.

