3.3 Enrollment

The target enrollment for this study is 25 patients with painful neuropathy symptoms (Group A) that develop during chemotherapy and 25 patients without painful symptoms during chemotherapy treatment (Group B). Final group assignment takes place on study day 1 when the patient takes a pain questionnaire. There are no differences in study activities between Group A and B. The Stanford Women's Cancer Center sees about 150 new cases of ovarian cancer per year, therefore we believe will able to complete enrollment in 12 months. Patients will be stratified into painful versus painless group based on their first pain assessment inventory. Based on the incidence of painful versus painless neuropathy, we anticipate that Group B will complete enrollment first. Should enrollment in Group A be very slow, our team will consider advertising outside of the Stanford Women's Cancer Center. An additional approach is to increase enrollment in Group B and apply an "unbalanced" design which would increase the number of patients in Group B, but still ensure statistical power of 80%. For example, if only 18 patients with pain are identified, enrolling 39 patients without pain will maintain 80% power. If this step is needed, we will amend the IRB as well as this application. Additionally, we will apply for a no-cost extension to the NIH SBIR that is funding the project.

We understand that patients participating in non-interventional, longitudinal, clinical studies may not follow up for a variety of reasons. To address possible drop out, patients will receive higher compensation for participation in the second test, 75 dollars for the first, 125 dollars for the second. A commonly anticipated drop-out rate is 20% (45), leaving us with approximately 40 patients who we anticipate will complete both time points within the study timeframe. However, it is possible that patients in pain (Group A) may be more likely to follow up with the second test, which would help preserve the power of the study.

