5.2 Analysis plan

The A δ :C pain threshold ratio will be recorded for each eligible and evaluable patient for both time points. We will calculate the average value of this parameter for each group (A and B) on a logarithmic scale. Then we will use a standard statistical two side t-test to compare the “A δ :C pain threshold ratio” in the painless CIPN group to the painful CIPN group. We hypothesize that the painful CIPN group will have statistically significantly higher value “A δ :C pain threshold ratio” than those without.

To assess whether the “A δ :C pain threshold ratio” predicts future painful or painless CIPN, we will conduct logistic regression analysis of the binary pain value (pain or no pain) at the time of the second testing (independent variable) on the “A δ :C pain threshold ratio” at the time of the first testing (dependent variable). It will allow us to estimate whether the “A δ :C pain threshold ratio” predicts the chances of a patient to develop pain.

As an exploratory analysis, we will explore if the “A δ :C pain threshold ratio” obtained at

the first testing session predicts an increase in the numeric pain scale at the second testing session.

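### Aim 2 relates the visit-1 ratio to visit-2 pain without visit-1 pain status, so a positive result may reflect pain already present rather than pain that develops

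*Combined protocol and SAP*

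**What the plan says.** Section 1.0 proposes that the ratio measured during chemotherapy "will identify those patients at risk of developing pain during their treatment". Section 5.1.2 labels the Aim 2 outcome as a correlation with the development of pain. The statistic it specifies is a Spearman coefficient between the ratio "obtained at the first testing session and the presence or absence of pain at the time of the second test".

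Section 5.2 adds a "logistic regression analysis of the binary pain value (pain or no pain) at the time of the second testing (independent variable") on the visit-1 ratio, which is labelled the dependent variable. It reads the result as showing whether the ratio "predicts the chances of a patient to develop pain". An exploratory analysis asks whether the ratio from "the first testing session predicts an increase in the numeric pain scale at the second testing session".

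On who is in the sample, section 3.2 (Inclusion Criteria) states: "GROUP A (painful neuropathy group): Must have subjective symptoms of painful peripheral neuropathy". Section 3.3 adds: "Final group assignment takes place on study day 1 when the patient takes a pain questionnaire". The study calendar in section 4.2 puts the first DLss test at that same visit. The target is 25 patients in each group. The most unbalanced row of Table 5.1 has 17 with pain and 42 without. Section 3.3 assumes 20% drop-out, "leaving us with approximately 40 patients who we anticipate will complete both time points".

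**The concern.** Patients in Group A cannot newly develop pain after visit 1, because they already have it when the predictor is measured. Aim 1 hypothesises that they also have the higher ratio. If some of that pain is still there about 12 weeks later (week 9 to week 21), the visit-1 ratio and visit-2 pain will be associated through visit-1 pain alone. The more convincingly Aim 1 succeeds, the more likely Aim 2 is to look positive for this reason.

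The study is meant to support a larger validation study of the ratio as a predictor. A pooled result could be carried forward as evidence of prediction when it shows only that the ratio tracks current pain, which Aim 1 already tests.

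**Working it through.** **Inputs from the protocol.** Group difference 1.31-fold and log-scale SD 0.33 (section 5.3); 25 + 25 or 17 + 42 patients (section 5.3, Table 5.1); drop-out 20% (section 3.3). Completers: 0.8 × 25 = 20 per group, or 0.8 × 17 = 13.6 ≈ 14 and 0.8 × 42 = 33.6 ≈ 34.

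**Assumptions.** Two-sided alpha 0.05; equal drop-out in both groups; *p* = probability that visit-1 pain is still present at visit 2 (persistence); *q* = probability of new pain in Group B (onset). The protocol gives none of alpha, *p* or *q*, so a range of *p* and *q* is shown.

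**Step 1: the plan's own figure.** The protocol states no power for Aim 2. For Aim 1, a two-sided t-test with 25 + 25, ln 1.31 = 0.270 and SD 0.33 has 80.9% power, which reproduces the stated 80%. (The log-scale effect printed in section 5.3, 0.24, is not ln 1.31 and gives 71.2%. I use 0.270.)

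**Step 2: the association induced by visit-1 pain.** Suppose the ratio carries no information beyond visit-1 group. With equal groups, the share of Group A is *p*/(*p* + *q*) among patients with visit-2 pain and (1 − *p*)/(2 − *p* − *q*) among those without. The expected difference in mean log ratio between them is 0.270 × [*p*/(*p* + *q*) − (1 − *p*)/(2 − *p* − *q*)].

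At 80/20 this is 0.270 × (0.80 − 0.20) = 0.162, an apparent 1.18-fold difference in the ratio between patients with and without later pain. At 50/50 it is zero.

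**Step 3: how often the planned test is significant.** Simulation with 10,000 trials per row (simulation error at most √(0.25/10,000) = 0.5 points). Log ratio = group × ln(fold) + N(0, 0.33²); visit-2 pain is drawn from visit-1 group only; likelihood-ratio logistic test.

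| Persistence / onset | Induced fold (20 + 20) | Pooled, 20 + 20, 1.31-fold | Pooled, 14 + 34, 1.31-fold | Pooled, 20 + 20, 1.15-fold |
|---|---|---|---|---|
| 50 / 50 | 1.00 | 6% | 6% | 6% |
| 60 / 40 | 1.06 | 9% | 9% | – |
| 60 / 20 | 1.12 | 18% | 17% | – |
| 70 / 30 | 1.11 | 18% | 16% | 9% |
| 80 / 20 | 1.18 | 34% | 30% | 14% |
| 90 / 10 | 1.24 | 53% | 50% | 20% |

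With visit-1 pain status in the model the rate is 6–7% throughout. If the ratio does not differ by visit-1 pain, the pooled rate is about 6%.

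The planned Spearman test behaves alike: in a separate run of 1,000 trials per scenario (20 + 20, 1.31-fold) it was significant in 15% at 70/30, 29% at 80/20 and 51% at 90/10. Section 5.3 expects an effect above 1.31. At 1.58-fold (its CIPN-versus-healthy figure, so an upper illustration) both planned tests reach 62% at 80/20.

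**Step 4: precision of the analysis that does address onset.** In Group B alone, with 20 completers and an assumed 4 new cases, SE = 0.33 × √(1/4 + 1/16) = 0.184. Power for a 1.31-fold difference (t-test on log ratio) is 28%, and an observed 1.31 would have a 95% CI of about 0.90 to 1.9. With 6 cases, SE = 0.33 × √(1/6 + 1/14) = 0.161, power is 36%, and the CI is about 0.94 to 1.8. With 34 Group B completers and 7 to 10 cases, power is about 47–56%.

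**The case against.** **The pooled test is valid for what it tests.** In every row above 6%, visit-1 ratio and visit-2 pain truly are associated, so the percentages are not type I error rates. This stands. The problem lies in what the plan concludes from the test, not in its null distribution. Section 5.2 also introduces the regression as predicting future painful or painless CIPN, which a marginal model can address.

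**Development could be counted from the start of chemotherapy.** Neuropathy before the first dose is an exclusion, so all neuropathic pain at week 21 arose during the study regimen. That softens the wording, but Group A's ratio is still measured after onset and so cannot have predicted it.

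**Persistence is a stated interest.** Sections 1.0 and 2.0 say so, and it is a legitimate question. Section 1.0 separates chronic painful, chronic painless and resolving courses, whereas section 5 merges onset and persistence in one test and gives no model for those courses.

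**The exploratory analysis uses change from visit 1.** It is a partial safeguard only: it is exploratory, pools both groups, and uses a scale for overall pain.

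**The size is assumed, and this is a feasibility study.** Both are true. The effect runs from nothing to 53%, and the Group B analysis is weak. That argues for an interval and a modest claim rather than for answering a different question.

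**Visit-1 pain status is itself unclear.** Section 3.2 applies the cut-off of 10 to the neuropathic pain questionnaire; section 4.4 applies it to the overall numeric scale. This stands, and any adjusted analysis needs it settled.

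**Conclusion.** The concern holds. As planned, Aim 2 cannot separate prediction of new pain from recognition of pain already present, although the text claims the former. That limitation is structural and does not depend on any assumed rate.

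How often it would mislead does depend on assumptions: alpha 0.05, equal drop-out, the 1.31-fold difference, no within-group association, and persistence and onset rates that the protocol does not give. On those terms the pooled logistic test is significant in 18% of trials at 70/30, 34% at 80/20 and 53% at 90/10. It is not inflated if pain does not persist or the ratio does not differ by visit-1 pain. This should be fixed before analysis.

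**What to change.** Amend section 5.2, and section 5.1.2 to match:

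1. Fit the logistic regression with visit-2 pain as the dependent variable, and log visit-1 ratio plus visit-1 pain status (Group A or B) as independent variables. Describe its odds ratio as added value over current pain. This also corrects the reversed labels.
2. Base any statement about development of pain on Group B only, and report persistence in Group A separately. Give each as an odds ratio or, more stably with few cases, as a ratio of geometric means of the visit-1 ratio, with a 95% confidence interval.
3. Make the pooled Spearman coefficient descriptive.
4. Give visit-2 pain risks within each group. A single pooled risk would reflect the recruitment quota.
5. State which scale and cut-off define pain status at both visits, reconciling sections 3.2 and 4.4.
6. State the expected precision of the Group B analysis.

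The cost is SAP wording and a few lines of code, since visit-1 pain status is already collected. The price is precision: Step 4 gives it for Group B. The adjusted all-patient model has about 65% (70/30), 53% (80/20) or 35% (90/10) power for a true 1.31-fold within-group difference, but assumes the same slope for onset and persistence. If only the minimum is changed, add the covariate and describe the pooled result as association with pain at week 21.
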